2.2 Secondary Objectives

2.2.1 To determine impact of PRO monitoring with symptom alerts compared to PRO monitoring without symptom alerts after thoracic surgery on post-operative readmission and mortality rates by analyzing:

1. 30-day post-discharge emergency department visit rate
2. 90-day post-discharge emergency department visit rate
3. 30-day post-discharge readmissions rate
4. 90-day post-discharge readmissions rate
5. 30-day mortality (percentage)
6. 365-day mortality (percentage)
7. Change in 2-year quality of life

2.2.2 To determine feasibility of PRO monitoring after thoracic surgery in regards to monitoring long-term quality of life. Feasibility is defined as $\geq 50\%$ of patients completing all quality of life surveys at baseline and all follow-up time points.

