7.0 STATISTICAL CONSIDERATIONS

7.1 Study Design

This is a single center, randomized feasibility study. A total of 140 patients undergoing thoracic surgery will be prospectively enrolled and randomized in a 1:1 ratio. A random block method with blocks of 20 will be utilized to randomize participants to one of two arms to complete PRO (patient reported outcome) symptom monitoring. The two arms are 1) active symptom monitoring and 2) passive symptom monitoring. The participants randomized to active symptom monitoring will have alerts sent to their clinicians when their PRO symptom scores exceed baselines scores by 2 points or more, or when 'severe' or 'very severe' symptoms are reported. Participants randomized to the passive PRO monitoring arm will complete the same PROs as participants in the active monitoring arm, but will not have alerts sent to their clinician. All participants will be administered survey instruments to further assess quality of life including: EORTC QLQ30, EORTC LC13, PROMIS Physical Function SF 4a survey SF 4a. Additionally, in order to assess the feasibility of the PRO monitoring system, all participants will be asked to complete a Patient Satisfaction survey. In addition, a subset of 40 participants and 40 caregivers will be chosen to complete a semi-structured interview, if willing, to assess patient satisfaction with symptom monitoring experience. The subset will be made up of a range of post-operative experiences and will be a fair representation of study population, including both

study arms. Participants will be chosen by principal investigator and eligible to participate in interview after 14 days of discharge

The primary objectives are to determine 1) impact of PRO monitoring with symptom alerts compared to PRO monitoring without symptom alerts after thoracic surgery on post-operative quality of life 2) feasibility of 3-month post-operative PRO symptom monitoring after thoracic surgery symptom monitoring eliciting a clinician response 3) barriers/facilitators of PRO monitoring after thoracic surgery through semi-structured interviews of patients.

Secondary objectives include: 1) determining impact of PRO monitoring with symptom alerts compared to PRO monitoring without symptom alerts after thoracic surgery on post-operative readmission and mortality rates 2) determining feasibility of PRO monitoring after thoracic surgery in regards to monitoring quality of life.

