7.2 Sample Size and Accrual

We originally anticipated 100-150 patients to be enrolled per year. A sample size of 66 in each group will have 80% power to detect a difference in mean EORTC scores of 10.000 assuming that the common standard deviation is 22.900 using two group t-test with a 0.050 one-sided significance level. The target sample size was 140 patients to allow appropriate block randomization in groups of 20. Based on enrolling about 140 patients, we would be powered to detect an effect size of 0.437 (difference in means of 10, common standard deviation of 22.9). Due to slower accrual in context of COVID-19, we anticipate enrollment of 100-140 patients before funding ends. With 100 patients, we will have 80% power to detect an effect size of 0.501 (difference in means of 11.467, common standard deviation of 22.9). Power calculations were performed using SAS version 9.4 (SAS Inc., Cary, NC) using PROC POWER and a two sample means difference test.

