7.3.3 Aim 3: Identify barriers/facilitators of PRO monitoring through semi-structured interviews.

Patient and caregiver interview transcripts will be analyzed as they are collected. Transcripts will be coded using in vivo coding methods and a code book will be created. Interviews will continue until thematic saturation is achieved, which will be defined by no new codes being generated to add to the code book.

7.3.4 Sub-Aim 1: Impact of PRO monitoring with symptom alerts, compared to PRO monitoring without symptom alerts, on post-operative readmission and mortality rates.

Kaplan Meier curves and Cox proportional hazards regression will be used to assess the impact of study treatment arm on 30-day and 90-day emergency department (ED) visits, readmissions, and all-cause mortality, as well as 1-year all-cause mortality. A linear mixed effect model will be used to assess the change in 2-year quality of life (described in Aim 1).

Patients who are lost to follow-up will be censored at their last clinician/study interaction. Mortality will be treated as a competing risk for ED visits and readmission. This aim will be approached as an intent-to-treat analysis and will not require that patients used their PRO monitoring or had symptom alerts sent to

their clinician.

7.3.5 Sub-Aim 2: Determine the feasibility of PRO monitoring for assessing quality of life.

Similar methods to Aim 2 will be used. The proportion of completed QOL surveys (overall and in each arm) at each time point (baseline/pre-operative and 2-weeks, 6-months, 1-year, and 2-year post-operative) will be calculated, as well as the proportion of participants who completed all surveys during that time. Chi-square, Student's T, and Wilcoxon rank sum tests will be used to compare patient demographics, study arm, and surgery characteristics between those who did and did not complete all surveys to attempt to identify predictors of compliance. Multivariable logistic regression may also be used.

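### Cox regression is the only between-arm comparison planned for mortality, and it gives no finite hazard ratio if an arm has no deaths; a risk difference should be the main summary for early mortality.

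*Combined protocol and SAP*

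**What the plan says.** Section 7.3.4 (Sub-Aim 1) states that "Kaplan Meier curves and Cox proportional hazards regression will be used" to assess the effect of study arm on "30-day and 90-day emergency department (ED) visits, readmissions, and all-cause mortality, as well as 1-year all-cause mortality". It names no other method for comparing mortality between the arms. Patients lost to follow-up are censored at their last contact.

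The matching objective, section 2.2.1, is comparative: "To determine impact of PRO monitoring with symptom alerts compared to PRO monitoring without symptom alerts after thoracic surgery on post-operative readmission and mortality rates". The mortality measures listed under it are "30-day mortality (percentage" and "365-day mortality (percentage", each with the percentage as the metric. Mortality at 90 days is not on that list.

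Section 7.1 plans that "A total of 140 patients undergoing thoracic surgery will be prospectively enrolled and randomized in a 1:1 ratio". Section 7.2 adds that "we anticipate enrollment of 100-140 patients before funding ends", so the arms will have 50 to 70 patients each.

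Neither section 7.2 nor section 7.3 gives an expected mortality rate or number of deaths. Section 7.3.1 provides a fallback if the mixed model for quality of life does not converge. Section 7.3.4 provides none for the Cox model.

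**The concern.** With a single arm indicator, the Cox partial likelihood has no finite maximum when all deaths fall in one arm. The estimated log hazard ratio runs to plus or minus infinity, and the standard interval that software prints cannot be used. With no deaths in either arm, there is nothing to fit.

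In a trial of 100 to 140 elective surgical patients this can plausibly happen at 30 days. The team would then have to choose another comparison after seeing how the deaths fell. That is avoidable, because a comparison of percentages gives an estimate and an interval at any death count and uses the metric that section 2.2.1 states.

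**Working it through.** **The plan's own figures.** The plan states no figure for mortality. Its sizing is for quality of life: "A sample size of 66 in each group will have 80% power to detect a difference in mean EORTC scores of 10.000", with SD 22.9 and a one-sided 0.05 test. The exact t-test power is 0.797 at 65 per arm and 0.803 at 66, so 66 reproduces. It says nothing about deaths.

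**Inputs.** Arm sizes n = 70 (section 7.1) and n = 50 (lower end of the range in section 7.2). The mortality rate p by the horizon is my assumption, from 1% to 5%, equal in both arms. The documents do not say whether mortality is counted from surgery or from discharge. If it is from discharge, in-hospital deaths drop out and the early rate is lower.

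**Chance of an empty arm.** With deaths per arm binomial (n, p), one arm has no deaths with probability (1 − p)^n. At least one of two arms has none with probability

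P = 1 − [1 − (1 − p)^n]².

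For p = 1%, n = 70: 0.99^70 = 0.495; 1 − 0.495 = 0.505; 0.505² = 0.255; P = 0.745.

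| Assumed p | Expected deaths, N = 140 | P, 70 per arm | Expected deaths, N = 100 | P, 50 per arm |
|---|---|---|---|---|
| 1% | 1.4 | 75% | 1.0 | 84% |
| 2% | 2.8 | 43% | 2.0 | 60% |
| 3% | 4.2 | 22% | 3.0 | 39% |
| 5% | 7.0 | 5% | 5.0 | 15% |
| 8% | 11.2 | 1% | 8.0 | 3% |

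**If the alerts work.** With 2% in one arm and 1% in the other, P = 1 − (1 − 0.98^n)(1 − 0.99^n), which is 62% at n = 70 and 75% at n = 50.

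**No deaths in either arm.** The probability is (1 − p)^(2n). With N = 140 it is 25% at 1%, 6% at 2% and 1% at 3%.

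**When the hazard ratio is finite.** With four deaths split two and two, the log hazard ratio has a standard error of about √(1/2 + 1/2) = 1. The 95% interval is then a factor of exp(1.96) ≈ 7 in each direction. At 5% mortality, power for a hazard ratio of 0.5 (two-sided 0.05) is 12% with 100 patients and 15% with 140. For 80% power, 4(1.960 + 0.842)²/(ln 0.5)² = 65.3, so 66 deaths, would be needed.

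**What a percentage gives.** The exact two-sided 95% upper limit is 1 − 0.025^(1/n), which is 5.1% for 0 of 70 and 7.1% for 0 of 50. It is informative with no deaths at all.

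**Contrast with readmission.** The background (section 1.2) cites 18% readmission at 90 days. That implies 18 to 25 events, and the chance of an empty arm is about 0.01% even with 50 per arm. The problem is specific to mortality.

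**The case against.** - **The death rate is assumed.** This stands. A reader might infer that the plan expects only a few deaths, or that the Cox model will usually fail. The documents support neither, since they give no mortality rate. At 5% the chance of an empty arm is 5% to 15%, and at 8% it is 1% to 3%. Cumulative deaths can only stay level or rise with time, so the risk is smaller at 90 days and at 1 year.
- **The objective does not ask only for a percentage.** This also stands. Section 2.2.1 asks for the effect of alerts against no alerts, so a between-arm model is not foreign to it. The percentage is the metric, and a risk difference answers both parts.
- **Kaplan-Meier already supplies percentages.** It does so even in an arm with no deaths, so it would be wrong to say that the mortality result is lost. What it does not supply, as planned, is a between-arm difference. In an arm without deaths the usual Greenwood standard error is also zero, so the interval collapses to a point.
- **The plan does not prescribe a Wald interval.** True. With deaths in one arm only, score and likelihood-ratio tests can be computed, and a profile-likelihood interval has one finite limit. There is still no finite estimate.
- **A crude risk difference ignores censoring.** This stands, because section 7.3.4 provides for censoring. The replacement needs a denominator rule.
- **The consequence is small.** Mortality is a secondary objective of a single-center feasibility study, and no power claim or decision rests on it.

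**Conclusion.** The point holds as a minor one. The only planned between-arm estimate for mortality may not exist when the trial is analysed, and nothing is specified to replace it. For an assumed rate of 1% to 3%, the chance of this is 22% to 75% with 70 per arm and 39% to 84% with 50. At 5% it falls to 5% and 15%. These figures rest on the assumed rate, equal risk in the arms and complete follow-up to the horizon. They bear mainly on 30-day mortality.

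The finding does not extend to emergency department visits or readmissions, and it does not mean that the mortality objective cannot be met. Separately, sections 2.2.1 and 7.3.4 disagree on whether 90-day mortality is an endpoint.

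**What to change.** Amend section 7.3.4 as follows.

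1. **30-day mortality:** make the main summary the number of deaths, the percentage per arm and the risk difference with an exact or score-type 95% interval. Name the interval method in advance; score intervals are approximate, though they remain computable with an empty arm.
2. **Denominator:** use patients whose vital status at the horizon is known. If any patient is censored earlier, give the Kaplan-Meier percentage.
3. **90-day mortality:** reconcile 7.3.4 with 2.2.1, which does not list it. If it is kept, treat it as at 30 days.
4. **365-day mortality:** report Kaplan-Meier percentages and their difference. If an arm still has no deaths, use the 30-day method for the interval.
5. **Hazard ratio:** fit any mortality hazard ratio by Firth's penalized likelihood with a profile-likelihood interval, as a supporting result. If there are no deaths in either arm, report none.
6. State the expected mortality rate and the time origin.

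The cost is a few sentences and little programming, with no change to data collection or sample size. The downsides are small: the hazard ratio is no longer the main comparison of early mortality, and the denominator rule for censored patients has to be fixed before analysis.

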Medical chart abstraction will be collected any time after enrollment to capture

clinical events as specified in the protocol.

Semi-Structured Interviews

The PI will identify patients to approach for semi-structured interview. Interviews may also be done with selected participants' caregivers. After the initial participant interviews have been completed, the caregiver interview guide, sampling frame and timeline will be submitted to the IRB once determined. Semi-structured participant interviews will initially be conducted between 14-90 days post-discharge. Sequential interviews will be conducted with the goal to complete 10 interview participants in the 14-90 days post-discharge PRO monitoring phase. Once complete or if there are no more participants in the 14-90 days post-discharge phase, the participants will be chosen purposively to capture patients with varying postoperative experiences and low PRO survey completion rates. Patients who completed the 90-days post-discharge symptom surveys but are in long-term follow-up to 12 months post-discharge may also be interviewed to increase the sample size as the study nears the end of enrollment, as needed. Interviews will be administered using interview guides and will continue until thematic saturation is achieved, which will be defined by no new codes being generated to add to the codebook. Semi-structured interview duration is dependent on individual participant responses, but the duration is expected to be approximately 30-60 minutes. The sample size is anticipated to be approximately 40 interviews with patients. An additional 40 interviews will be conducted with selected participants' caregivers for those participants who agree to have caregivers contacted. The participants who are asked to be interviewed will receive a \$20 gift card for their participation after completion of the interview.

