4.5 Removal of Patients from Protocol

Patients will be removed from the study if:

- they experience significant emotional distress in response to PRO surveys
- they indicate that they no longer wish to participate

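### Censoring lost patients at last contact, while chart-found ED visits and readmissions may still count, can inflate the 30- and 90-day event estimates (minor, secondary endpoints)

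*Combined protocol and SAP*

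**What the plan says.** Section 7.3.4 sets the method: "Kaplan Meier curves and Cox proportional hazards regression will be used to assess the impact of study treatment arm on 30-day and 90-day emergency" department visits, readmissions and all-cause mortality, with one-year mortality added. It then states "Patients who are lost to follow-up will be censored at their last clinician/study interaction", and "Mortality will be treated as a competing risk for ED visits and readmission". Neither loss to follow-up nor interaction is defined. The section also says "This aim will be approached as an intent-to-treat analysis", and adds that patients need not have used the monitoring.

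On where events come from, section 4.3 says "Medical chart abstraction will be collected any time after enrollment to capture" clinical events. It gives no date through which each chart is reviewed and no link to the censoring date. Section 4.3 also schedules a Readmission Patient Survey.

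On what differs between arms, section 7.1 has both arms complete the same PROs. Passive-arm participants "will not have alerts sent to their clinician". Section 4.3 gives one symptom-survey schedule for everyone: daily to Day 14, then weekly to Day 90.

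The plan does not say how a chart event dated after the last interaction is handled, and it gives no expected loss rate.

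**The concern.** The rule can treat two lost patients differently according to their outcome. One who stops responding and is later readmitted has, by that readmission, a further clinician interaction, so follow-up runs to the event and the event counts. One who stops responding and stays well is cut off at the earlier contact. Follow-up length then depends on whether the event happened. The risk set loses only people who would have remained event-free, and both Kaplan-Meier and Cox estimates of event frequency move upward.

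The ED visit and readmission rates are listed endpoints in section 2.2.1, so their level matters even if the arms are affected equally. A second question is whether alert responses, which only the active arm can have, move the censoring dates apart and so disturb the comparison.

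**Working it through.** **Plan figure.** Section 7.2 gives only a sizing for the QOL comparison: 66 per group. It reproduces (noncentral t, one-sided 0.05, difference 10, SD 22.9: power 80.3%). It does not bear on readmission. The plan gives no figure for loss or event counts.

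**Inputs.** The 90-day readmission rate is 18% (section 1.2), used as the true rate in both arms. There are 140 patients at 1:1, so 70 per arm (section 7.1). Assumptions not in the documents: event times exponential; a share p of patients lost, at times uniform over 90 days; chart events after loss all found. Death as a competing risk is not modelled.

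**Step 1: level of the estimate.** Let u = day/90. The cumulative hazard to Day 90 is -ln(0.82) = 0.1985, and S(u) = exp(-0.1985u). By time u the rule has removed only lost patients who stay event-free to Day 90, a share p × u × 0.82. The hazard is therefore multiplied by

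r(u) = 1 / (1 - p × u × 0.82 / S(u)),

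and the estimate is 1 - exp(-0.1985 × mean of r). The mean is taken by Simpson's rule at u = 0, 0.5 and 1.

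| p (both arms) | r(0), r(0.5), r(1) | mean r | cumulative hazard | 90-day estimate |
|---|---|---|---|---|
| 0% | 1, 1, 1 | 1.000 | 0.1985 | 18.0% |
| 10% | 1, 1.047, 1.111 | 1.050 | 0.2084 | 18.8% |
| 20% | 1, 1.100, 1.250 | 1.108 | 0.2199 | 19.7% |
| 30% | 1, 1.157, 1.429 | 1.176 | 0.2334 | 20.8% |

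The same mechanism acts on the 30-day estimates. The documents give no 30-day rate, so no figure is computed.

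**Step 2: ratio between arms.** The estimate depends only on p, so equal loss gives a ratio of 1.00. An imposed 10% v 20% loss (active v passive) gives 18.8/19.7 = 0.95, and 10% v 30% gives 18.8/20.8 = 0.90. These ratios come entirely from the assumed inequality.

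**Step 3: alert contacts modelled directly, no true effect.** Simulation on the protocol's survey schedule, with alerts arising only from completed surveys and 10-30% loss. Assumptions: 70% survey completion, alerts on 15% of completed surveys (high case 30%), half of alerts answered (high case all), response delay 0-3 days (high case 0-30).

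- Survey submissions count as interactions: lost patients censored on average near day 39.5 (passive) and 39.9 (active); hazard ratio 0.99-1.01.
- Only assumed clinic contacts at Days 14 and 60 and alert responses count: about day 27 v 29; hazard ratio 0.99-1.00.
- High case: 0.97-0.99 if surveys count, 0.94-0.98 if they do not.
- Extreme bound, lost passive patients cut at day 1 and lost active patients at day 90: 0.91, 0.82 and 0.73 at 10%, 20% and 30% loss.
- Opposite direction: if 10%, 20% or 30% of readmissions are at outside hospitals, become known for 50% (passive) v 80% (active), and unknown ones are treated as event-free, the ratio is 1.03, 1.07 or 1.12.

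**Step 4: what removes the distortion.** If events and time both stop at last contact, the event rate and the risk set are each multiplied by (1 - p × u). The factor cancels and the estimate is 18.0%, provided contact times are unrelated to readmission risk. If everyone is followed by chart to Day 90, p drops out and the estimate is again 18.0%.

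**Step 5: scale.** Expected readmissions are 70 × 0.18 = 12.6 per arm. The 95% limits on a hazard ratio near 1 are a factor of exp(1.96 × √(1/12.6 + 1/12.6)) = exp(0.78) ≈ 2.2 either way.

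**The case against.** A reader might infer that the rule makes readmission look lower in the active arm. The documents do not support that. Both arms follow the same survey schedule, and an alert can arise only from a completed survey, which is arguably already a study interaction. A patient who has stopped responding generates no new alerts, so the extra follow-up is normally just the response delay. No section gives a loss rate or suggests that loss will be unequal. Alert calls that reveal outside readmissions would push the ratio the other way.

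It can also be said that section 7.3.4 never states that chart events after last contact are counted. If events and time at risk stop on the same date, there is no bias from unequal contact alone. This is fair: the inflation is conditional. But counting such events is the natural reading, because a readmission is a clinician interaction, and the alternative means discarding known readmissions, which the plan does not state.

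A reader might further see a contradiction with intent-to-treat. There is none. Intent-to-treat fixes analysis by assigned arm, and censoring at last contact is conventional. Nor is a survey non-responder necessarily lost, since a patient still seen by a clinician has interactions.

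Finally, these are secondary endpoints in a feasibility study sized on QOL. That stands, and it sets the severity.

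**Conclusion.** The concern holds as a minor one. The rule is incomplete and, on its natural reading, asymmetric. If later chart events count while event-free lost patients stop at last contact, a true 18% 90-day readmission rate is estimated at about 18.8% with 10% loss and 19.7% with 20% loss in both arms. The loss rates and uniform loss times are assumptions.

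The between-arm ratio stays near 1.00 unless loss or contact differs by arm. Under plausible assumptions about alert contacts the shift is about 0-6% on the hazard ratio, the upper end needing the high case, and it can go in either direction. Against an interval spanning a factor of about 2.2 each way, it would be unlikely to change a conclusion. The primary QOL comparison is not affected.

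**What to change.** In section 7.3.4:

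- Define loss to follow-up and interaction, and use one cut-off for both events and time at risk, the same in both arms.
- Follow every randomized patient by the planned chart abstraction to Day 30, 90 and 365, including those who stop surveys or are removed under section 4.5, unless consent for chart review is withdrawn. Censor event-free patients at the horizon, or at the date through which the chart was reviewed if earlier.
- State that survey and alert-triggered contacts do not set the censoring date.
- As a sensitivity analysis, count both events and time only up to last contact.
- Use the Readmission Patient Survey in both arms as a supplementary source, and report events by source.

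The cost is a few sentences and a uniform chart sweep. The downside is that outside-hospital events may be missed, possibly unequally by arm if alert calls reveal them. As a check, suppose 25% of readmissions are outside and unseen after loss, with loss of 10-40%. The common horizon then gives 17.1-17.8%, with ratios of 1.01-1.03 under unequal loss. The asymmetric reading of the current rule gives 18.5-21.0%, with ratios of 0.92-0.96. The horizon rule stays closer to the true 18% and 1.00.

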1.2 Background

Patient-centered outcomes after surgery go beyond traditionally measured morbidity and mortality to include QOL [11]. Patients undergoing thoracic surgery strongly value communication from their providers about anticipated physical functioning post-operatively [12, 13]. Patients who require thoracic surgery are older, have comorbidities, and have greater decreases in QOL after often morbid treatments compared to other patients [14]. Therefore, 90-day readmissions after thoracic surgery remain high at 18%, largely due to symptomatic adverse events including post-operative complications and new cardiopulmonary diagnoses [4, 15]. While symptom severity and physical functioning worsen for up to 6 months after thoracic surgery [16-18], pain and QOL do return to baseline by 12 months [19], suggesting a window in the first year after surgery during which PROs can be better monitored and managed.

In non-surgical populations, management of patient-reported symptoms has been extensively linked to improvements in care delivery including readmissions. The NIH has developed a PRO version of the Common Terminology Criteria for Adverse Events (PRO-CTCAE), which is a validated library assessing the presence, frequency, severity, and interference with usual activities of symptoms. Responses are provided by patients on a 5-point Likert scale with recall being over the prior week [20]. PRO-CTCAE is feasible for use in a variety of patient populations [21]. In surgical patients, PROs have been used as clinical outcomes, for quality improvement, and as outcomes in comparative effectiveness research [22]. In thoracic surgery patients specifically, PRO assessment through weekly

telephone surveys has demonstrated symptom improvement; however, items assessed were standard cancer-related and one surgical specific symptom. Further, only 60% of symptom alerts lead to intervention by clinicians [8].

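### Section 7.3.4 names Kaplan-Meier curves for ED visits and readmissions but calls death a competing risk for both, and names no estimator that treats it as one

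*Combined protocol and SAP*

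**What the plan says.** Section 7.3.4 (Sub-Aim 1) gives one set of methods for a mixed list of endpoints: "Kaplan Meier curves and Cox proportional hazards regression will be used". The list takes in ED visits, readmissions and deaths from any cause, each at 30 and 90 days, and deaths at one year. The next paragraph has two rules on incomplete follow-up. The first is on censoring: "Patients who are lost to follow-up will be censored at their last clinician/study interaction". The second is on death: "Mortality will be treated as a competing risk for ED visits and readmission".

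Section 2.2.1 lists the matching secondary endpoints as rates, for example "90-day post-discharge readmissions rate", with the same form for 30-day readmissions and for 30- and 90-day ED visits.

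Neither section 7.3.4 nor any other section mentions a cumulative incidence function or Gray's test, or says whether the regression models a cause-specific or a subdistribution hazard. No section says that deaths are to be censored in the ED-visit or readmission curves.

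**The concern.** Kaplan-Meier recognises one type of event. A patient who dies without having been readmitted has to be placed somewhere, and the usual practice is to censor at death. That treats the patient as someone who could still have been readmitted later, so one minus Kaplan-Meier is then at or above the proportion actually readmitted. The two are equal only if nobody dies first. The plan rightly identifies death as a competing risk for these two endpoints, but the curve it names for them does not, in its ordinary form, treat death as one.

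The regression has a different gap. A cause-specific hazard ratio and a subdistribution hazard ratio are both legitimate with a competing risk, but they answer different questions and can differ. The plan does not choose, so the choice could be made after the data are seen.

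At stake are the descriptive rates for four secondary endpoints and the meaning of the hazard ratio reported beside them.

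**Working it through.** **Plan's own figure.** There is none for this point. The only design calculation (section 7.2: 66 per group, difference of 10 in mean EORTC score, SD 22.9, one-sided 0.05) reproduces with a noncentral t calculation, at 80.3% power. It does not bear on ED visits or readmissions.

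**Inputs.**
- F, cumulative incidence of readmission by day 90: 18%. Section 1.2 says "90-day readmissions after thoracic surgery remain high at 18" percent. This is a background figure, used here for illustration.
- D, death without prior readmission by day 90: not in the documents. Assumed 1%, 2% and 5%, with 10% as an extreme.
- Arm size: 70, from 140 randomized 1:1 (section 7.1), or 50 if only 100 enroll (section 7.2 anticipates 100 to 140).

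**Formulas**, with constant cause-specific hazards over 90 days and deaths censored:
- Total cumulative hazard: H = -ln(1 - F - D)
- Readmission part: h = H × F/(F + D)
- One minus Kaplan-Meier at day 90: 1 - exp(-h)
- Excess: [1 - exp(-h)] - F

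**Results at day 90, F = 18%.**

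| Assumed D | H | h | 1 - KM | Excess (points) |
|---|---|---|---|---|
| 1% | -ln(0.81) = 0.2107 | 0.2107 × 18/19 = 0.1996 | 18.10% | 0.10 |
| 2% | -ln(0.80) = 0.2231 | 0.2231 × 18/20 = 0.2008 | 18.19% | 0.19 |
| 5% | -ln(0.77) = 0.2614 | 0.2614 × 18/23 = 0.2045 | 18.50% | 0.50 |
| 10% | -ln(0.72) = 0.3285 | 0.3285 × 18/28 = 0.2112 | 19.04% | 1.04 |

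**Day 30.** With the same hazards, one minus Kaplan-Meier is 1 - exp(-h/3) and the cumulative incidence is F/(F + D) × [1 - exp(-H/3)]. For D of 1% to 5% the excess is 0.01 to 0.06 points.

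**Timing of deaths.** The least favourable case puts all deaths at the start of follow-up. One minus Kaplan-Meier is then F/(1 - D); at D = 5% this is 0.18/0.95 = 18.9%, an excess of about 0.9 points.

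**ED visits.** The documents give no rate. With an assumed 90-day incidence of 10% or 30% and D = 5%, the constant-hazard excess is 0.27 or 0.87 points.

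**Against sampling error.** The standard error of an 18% rate is √(0.18 × 0.82/70) = 4.6 points with 70 per arm and √(0.18 × 0.82/50) = 5.4 points with 50. An excess of 0.50 points is 0.0050 × 70 = 0.35 of a patient in an arm of 70.

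**The case against.** The strongest reply is that the plan does not commit the error. Its censoring rule covers loss to follow-up only, and death has its own sentence. A specific rule for two endpoints can be read as qualifying a general sentence that also covers mortality. It is also possible to make the two statements agree: if patients who die stay in the risk set to day 30 or 90 and nobody else is censored earlier, one minus Kaplan-Meier equals the cumulative incidence. Further, the methods are introduced for comparing arms, and nothing says that one minus Kaplan-Meier will be reported as the rate in section 2.2.1; a simple proportion remains open.

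Much of this stands, and it rules out three readings that a reader might infer:

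- *The curves will overstate both rates.* This holds only if deaths are censored in them, which the plan does not say.
- *The two statements cannot both be followed.* This is true of ordinary Kaplan-Meier curves with deaths censored, but not of the regression. Cox with deaths censored is a standard cause-specific analysis under competing risks.
- *The comparison between arms is biased.* The documents do not support this. The cause-specific hazard ratio is a valid target.

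What does not stand is the inference that nothing needs changing. Kaplan-Meier is named explicitly for these two endpoints, and the competing-risk sentence is not accompanied by any method that would carry it out. An analyst following the named method in the usual way would censor deaths, against the plan's stated intention.

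**Conclusion.** The point holds as a minor inconsistency in specification. The curve named for ED visits and readmissions does not fit the plan's own statement about death, and the type of hazard in the Cox model is left open.

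If deaths are censored in the curves, the overstatement of 90-day readmission is about 0.1 to 0.5 percentage points. That assumes 18% readmission, death before readmission of 1% to 5%, and constant hazards. It would be about 1 point at 10% deaths and zero if nobody dies first. The mortality values are assumptions. Within the 1% to 5% range the excess is small beside a standard error of about 4.6 points. The endpoints are secondary, and no feasibility threshold in sections 2.1 or 2.2 depends on them. The reason to act is that the wording is easily made right, not that the results are at risk.

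**What to change.** In section 7.3.4:

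1. Replace Kaplan-Meier with cumulative incidence (Aalen-Johansen) curves for 30- and 90-day ED visits and readmissions, with death as the competing event, and read the rates in section 2.2.1 from these curves.
2. Keep Kaplan-Meier for all-cause mortality only.
3. State that the Cox model for ED visits and readmissions is cause-specific, with deaths censored, and is the main comparison between arms.
4. If Gray's test is also reported, call it supportive. It compares cumulative incidence, so it tests a different hypothesis from the cause-specific model and the two can disagree; the order needs to be fixed in advance.

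The cost is a few sentences and trivial analysis work, with no new data, visits or patients. Section 7.2 names software only for the power calculations, so the analysis software for this section could be stated at the same time.
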